5.8.3 Other Efficacy Endpoint(s) and Analysis

Other efficacy endpoints will be summarized by study phase (Double-blind Acute Phase, Open-label Acute Phase, and Double-blind Maintenance Phase) using the appropriate Safety Analysis Set for that phase.

5.8.3.1 UC-DAI

- The partial UC-DAI (continuous version, calculated as the sum of symptoms plus PGA score) and the full UC-DAI (continuous version, calculated as the sum of partial UC-DAI plus endoscopy) will be summarized by visit and treatment arm (as applicable) for each study phase. These tables will include both continuous and categorical summaries. Separate summaries will be produced for the full UC-DAI using endoscopy results from central and local readings.
- The components of the UC-DAI (average stool frequency score, average rectal bleeding score, PGA score and endoscopy score) will be summarized individually as continuous and categorical variables by visit and treatment arm (as applicable) for each study phase.

These tables will include separate summaries of endoscopy scores using results from central and local readings.

- The change from baseline to Week 2, Week 4, Week 8, and FoTA for the Double-blind Acute phase and change from Week 0 to Week 13 and Week 26 for the Double-blind Maintenance Phase for the components of the UC-DAI will be summarized individually as categorical variables by treatment arm (as applicable) using shift tables for each study phase.
- To examine concordance between PGA and endoscopy scores (central and local readings), cross-tabulations of the assessment results at each study visit will be displayed. A weighted Kappa statistic will be presented to serve as measure of the degree or amount of agreement between the two assessments.

5.8.3.2 PUCAI

- The PUCAI will be summarized by visit and treatment arm (as applicable) for each study phase. These tables will include both continuous and categorical [<10 (remission); 10-34 (mild); 35-64 (moderate) and 65 or above (severe)] summaries.
- The components of the PUCAI score (abdominal pain, rectal bleeding, stool consistency, number of stools in 24 hours, nocturnal stools, and activity level) will be summarized individually by visit and treatment arm (as applicable) for each study phase.

5.8.3.3 IMPACT III

- The IMPACT III domains (body image, bowel symptoms, emotional functioning, social functioning, systemic symptoms, and treatment/interventions) and total score and change from baseline will be summarized by visit and treatment arm (as applicable) for each study phase.

5.8.3.4 DUCS

- Listings of the responses to each of the items collected as part of the electronic daily sign and symptom diary (DUCS) will be presented by treatment, subject, visit, and visit date. These listings will include items for overall current health and global change in health.

5.8.4 Exploratory Efficacy Endpoint(s) and Analyses

- [REDACTED]
- [REDACTED]
- [REDACTED]

5.9 Analysis of Safety

All summaries of safety data will be produced separately for each phase of the study, for the Double-blind Acute Safety Analysis Set (overall and by treatment arm), Open-label Acute Safety Analysis Set (by treatment arm only), and Double-blind Maintenance Phase Safety Analysis Set (overall and by treatment arm).

Baseline is defined as the last observation prior to first dose of investigational product in the study. If an assessment occurs on same day as the first dose of investigational product, the assessment will be considered the Baseline assessment. The Double-blind Acute Phase Week 8/Withdrawal visit (Visit 3.2) is treated as the Open-label Acute Phase Week 0 for subjects continuing into the Open-label Acute Phase from this visit. The Double-blind Acute Phase Week 8/Withdrawal visit (Visit 3.2) is treated as the Double-blind Maintenance Phase Week 0 for subjects continuing into the Double-blind Maintenance Phase from this visit. The Open-label Acute Phase Week 8/Withdrawal visit (Visit 4.2) is treated as the Double-blind Maintenance Phase Week 0 for subjects continuing into the Double-blind Maintenance Phase from this visit. For subjects who enter the Double-blind Maintenance Phase directly, the Baseline Visit (Visit 2) is treated as the Double-blind Maintenance Phase Week 0.

Safety variables include AEs, clinical laboratory variables and vital signs variables. For each safety variable, the last value collected prior to the first dose of investigational product (during phase of interest) will be used as baseline/Week 0 for the analyses of that safety variable. A Final on-Treatment Assessment (FoTA) will be defined as the last valid assessment obtained after baseline/Week 0 and whilst on investigational product.

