1. BACKGROUND INFORMATION

1.1 Indication and Current Treatment Options

Ulcerative colitis (UC) is a serious chronic inflammatory disease of the colon and rectum. The major clinical feature is bloody diarrhea. While an acute attack can occasionally be fatal, the characteristic course for most patients is one of remissions and exacerbations over a number of years. Life expectancy after recovery from a first attack is unchanged; however, morbidity can be long-lasting and may be associated with various extra-intestinal and late complications.

Extensive disease is observed in 60-80% of all cases when UC onset is in childhood, which is twice as often as in adults. Extensive disease results in a worse disease course, since disease course is correlated to disease severity. In children, 30-40% colectomy rates are seen at 10 years compared to 20% in adults with UC (Turner et al. 2012). Children may also develop unique and troublesome complications, including growth failure and delayed puberty. Although infrequent and geographically dispersed, UC has been reported as early as infancy. Most children with UC, however, are diagnosed in late childhood and adolescence. The peak incidence of inflammatory bowel disease occurs in patients between the ages of 15 and 25 years. Approximately 20% of patients with UC present before the age of 20 years (Mendeloff and Calkins 1988). There are approximately 50,000 children currently with UC in the US, primarily post-pubertal.

Clinical pediatricians agree that mesalamine has a role in therapy of UC in children, and pediatric gastroenterology guidelines contain reference to mesalamine therapy in UC. The side effect profile of mesalamine is broadly similar to placebo, and there are no indications from the literature that use of mesalamine in children is associated with a higher incidence of side effects.

The only acetyl-5-aminosalicylic acid (5-ASA)/mesalamine product that is currently licensed in the US for use in children/adolescents (aged 5 years and older with UC) and that is available in non-tablet formulation is balsalazide (COLAZAL[®], Salix Pharmaceuticals, Inc) capsules. Balsalazide is a prodrug that is enzymatically cleaved in the colon to produce mesalamine. Capsule contents can be sprinkled on apple sauce if the capsules are too big to swallow.

The approval of 5-ASA products in other countries for use on children/adolescents varies.

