4.4.2 Vital Signs

Vital signs include blood pressure and pulse. Blood pressure should be determined by cuff (using the same method, the same arm, and in the same position throughout the study). Any clinically significant deviations from the Baseline Visit (Visit 2) vital signs which are deemed clinically significant in the opinion of the investigator are to be recorded as an AE.

Measurements of vital signs (blood pressure and pulse) will be performed at all study visits. Blood pressure and pulse will be determined in the sitting position (after 5 minutes).

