4.4.3 Height and Weight

Height will be assessed at the Screening Visit (Visit 1) and at the final visit of each phase. Weight will be assessed at the Screening Visit (Visit 1), the Baseline Visit (Visit 2) and at the final visit of each phase.

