5.5 Demographic and Baseline Characteristics

Descriptive summaries of demographic and baseline characteristics will be presented separately for each Safety Analysis Set (Overall, Double-blind Acute Phase, Open-label Acute Phase and Double-blind Maintenance Phase). For the Double-blind Acute Phase and Double-blind Maintenance Phase Safety Analysis Sets, summaries will be presented by treatment arm and overall. For the Overall Safety Analysis Set, summaries will be presented by overall, and for the Open-label Acute Phase Safety Analysis Set, summaries will be presented for high-dose only.

Demographic characteristics include age, age group (5-10 years and 11-17 years), sex, ethnicity, and race. Baseline characteristics include weight, weight group (18 to \leq 23kg, >23 to \leq 35kg, >35 to \leq 50kg and >50 to \leq 90kg), height, and body mass index (BMI). Height will be presented in cm and weight will be presented in kg. Any height measurements recorded in the CRF in inches will be multiplied by 2.54 to convert to cm. Body mass index will be presented in kg/m².

Ulcerative colitis history will be presented separately for each Safety Analysis Set (Overall, Double-blind Acute Phase, Open-label Acute Phase, and Double-blind Maintenance Phase). For the Double-blind Acute Phase and Double-blind Maintenance Phase Safety Analysis Sets, summaries will be presented by treatment arm and overall. For the Overall Safety Analysis Set, summaries will be presented overall only, and for the Open-label Acute Phase, summaries will be presented for high-dose only.

The following parameters will be summarized:

- Time (in months) since diagnosis ([screening date - diagnosis date] +1 / 30)
- Method of diagnosis
- Diagnosis state (i.e., is the subject newly diagnosed)

For subjects who are not newly diagnosed:

- Number of acute episodes of UC in the last year
- Number of acute episodes of UC since diagnosis
- Typical duration of past acute episodes (days [where this is recorded in weeks the value will be multiplied by 7])
- Time (in days) since current acute episode of UC ([screening date - onset date] +1)
- Full extent of disease measured from anal margin (cm) at the time of the most recent endoscopy
- The classification of the extent of disease at the most recent endoscopy
- Subjects with rectal involvement
- Subjects with extra-intestinal manifestations
- Subjects with any history of significant GI surgery

Medical history will be listed.

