5.9.3 Vital Signs

Descriptive statistics for vital signs (e.g., systolic and diastolic blood pressure, and pulse rate) and their changes from baseline/Week 0 at each post-baseline/Week 0 visit will be presented for Double-blind Acute and Double-blind Maintenance Phase Safety Analysis Sets, and also for Open-label Acute Phase Safety Analysis Set.

Vital sign values will be considered PCI if they meet either the low or high PCI criteria listed in [Table 3](#). The number and percentage of subjects with PCI post-baseline values will be tabulated. The percentages will be calculated relative to the number of subjects with baseline and at least 1 post-baseline/Week 0 assessment during phase of interest. The numerator is the total number of subjects with at least 1 PCI post-baseline/Week 0 vital sign value during phase of interest.

A supportive listing of subjects with post-baseline/Week 0 PCI values will be provided including the subject number, site, baseline/Week 0, and post-baseline/Week 0 PCI values.

Table 3: Criteria for Potentially Clinically Significant Vital Signs

Vital Sign Parameter	Age (yrs)		
		Lower Limit	Upper Limit
Systolic blood pressure (mmHg)	5 - 6	<89	>125
	7 - 12	<92	>135
	≥13	<100	>140
Diastolic blood pressure (mmHg)	5 - 6	<50	>84
	7 - 12	<55	>90
	≥13	<60	>90
Pulse rate (beats per minute)	5 - 6	<50	>130
	7 - 12	<50	>125
	≥13	<50	>120

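### The SAP plans no post-baseline summary or listing of measured height or weight, although both are end-of-phase safety assessments and Protocol 9.9 promises summaries of other safety parameters.

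*SAP*

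**What the plan says.** **Collection.** Height and weight stand under the safety headings of both documents (Protocol 7.2.2.3, SAP 4.4.3). SAP 4.4.3 states: "Height will be assessed at the Screening Visit (Visit 1) and at the final visit of each phase". For weight it states: "Weight will be assessed at the Screening Visit (Visit 1), the Baseline Visit (Visit 2) and at the final visit of each phase". Protocol 7.2.2.3 adds measurement standards: a calibrated stadiometer, one calibrated scale throughout, height recorded to 1 cm or half an inch, weight to 0.2 kg. The protocol history shows that Amendment 2 introduced the height measurements, the weight at the end of Maintenance and this section on standardisation.

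**Analysis.** SAP 5.9 defines the scope: "Safety variables include AEs, clinical laboratory variables and vital signs variables". SAP 4.4.2 says "Vital signs include blood pressure and pulse", and SAP 5.9.3 plans "Descriptive statistics for vital signs (e.g., systolic and diastolic blood pressure, and pulse rate") with changes from baseline/Week 0. Height, weight and BMI enter the analysis only through SAP 5.5: "Baseline characteristics include weight, weight group", followed by height and BMI, and "Height will be presented in cm and weight will be presented in kg".

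**Commitment.** Protocol 9.9, after dealing with AEs, laboratory tests and vital signs, says that the remaining safety parameters will also be summarised at each time point. SAP Section 6, which lists changes from the protocol's analyses, does not mention height or weight.

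**Context.** Protocol 1.1, in the disease background, says: "Children may also develop unique and troublesome complications, including growth failure and delayed puberty".

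**The concern.** The trial measures height and weight to a set standard in children aged 5-17 years, classes both as safety data, and then plans to show only the starting values. The study is a paediatric post-approval commitment with safety objectives in all three phases. A reader of the study report could not tell from the planned tables whether children on the low or the high dose gained or lost weight, or grew, over a phase.

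Weight change also bears on exposure. Under Protocol 7.1.1.3 the dose stays fixed within a phase when weight changes, so the mg/kg dose drifts, and SAP 7.7.1 models response on mg/kg.

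The mismatch with Protocol 9.9 makes this more than a missing detail. The protocol promises a summary, the SAP does not deliver it, and the SAP does not say so.

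**Working it through.** The question is whether any planned output shows height or weight after baseline. The protocol and SAP give no figure to reproduce, so the check compares texts and output titles. A short calculation on resolution follows.

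**Step 1: outputs in SAP Section 10 that could hold height, weight or BMI.**

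| Output | Content | Post-baseline height or weight? |
|---|---|---|
| Tables 14.1.4.2.1 to 14.1.4.2.4 | Baseline characteristics, four analysis sets | No |
| Listing 16.2.4.2.1 | Baseline characteristics by subject | No |
| Tables 14.3.5.1 to 14.3.5.6 | Vital signs: values, change, potentially clinically important (PCI) values | No: blood pressure and pulse under SAP 4.4.2 |
| Listings 16.2.8.2.1 and 16.2.8.2.2 | Vital signs and PCI vital signs | No, same definition |
| TEAE tables (14.3.1.x to 14.3.3.x) and Listing 16.2.7.1.1 | Reported AEs | Only if reported as an AE; no measured values |

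The count is four baseline tables, one baseline listing, and no legible title for measured follow-up values.

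**Step 2: could the baseline tables show end-of-phase values indirectly?** Visits 3.2 and 4.2 serve as Week 0 of the next phase, so a Week 0 reading of the Open-label or Maintenance baseline tables could show some of them. SAP 5.8, however, defines baseline as the last value before the first dose in the study. Even on the Week 0 reading, the values at Visit 5.2, the end of Maintenance, appear nowhere.

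**Step 3: is the omission recorded?** The changes in SAP Section 6 concern sensitivity analyses, the estimation wording, the acute sample size, subgroups, the Maintenance endoscopic endpoints and the DUCS psychometric analysis. None concerns height or weight.

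**Step 4: what could the data resolve?** The documents give no growth rate. As an illustrative assumption, take 4 to 7 cm/year before the end of puberty and about 0 afterwards.

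- Maintenance, 26 weeks: 4 × 26/52 = 2.0 cm to 7 × 26/52 = 3.5 cm.
- Acute phases, 8 weeks: 4 × 8/52 = 0.6 cm to 7 × 8/52 = 1.1 cm.
- Recording step for height: 1 cm, or 0.5 inch × 2.54 = 1.27 cm.
- Recording step for weight: 0.2 kg, which is 0.2/18 = 1.1% of body weight for the lightest eligible child (18 kg) and less for heavier children.

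Expected height change is therefore two to three and a half times the 1 cm step over Maintenance and about equal to it over 8 weeks. Weight is recorded finely enough to summarise in every phase.

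**Step 5: how many children?** Planned enrolment is 53 in the Double-blind Acute Phase and at least 80 in Maintenance (SAP 3.5). The groups overlap: 28 Maintenance subjects are expected from the acute phases. If that held, the plan covers at least 53 + 80 − 28 = 105 distinct children. The 28 also appears in the protocol beside an acute enrolment of up to 80, so it may not hold with 53. These are planned enrolments, not counts of completed measurements.

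**The case against.** **The AE route.** A reader might infer that growth or weight loss is not reported at all. The documents do not support that. Investigators assess conditions found at visits as possible AEs (SAP 4.4.1), changes on physical examination after screening become AEs at their discretion (SAP 4.4.7), and every TEAE is tabulated by system organ class and preferred term and listed. This stands, but the route depends on judgement, gives no measured change by arm, and has no growth or weight category among the events of special interest in SAP 5.9.1. It does not replace a summary.

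**Drug risk.** A reader might also infer that growth failure is a known risk of the treatment. Protocol 1.1 names it as a complication of the disease, and the same section describes mesalamine's side effects as broadly similar to placebo's. No growth objective appears in the legible text. This limits the seriousness of the point.

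**Another use for the weights.** Weight at Visits 3.2 and 4.2 sets the next phase's dose or randomisation stratum, so it is not idle data. That is true, but it does not apply to weight at the end of Maintenance or to any follow-up height.

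**Raw change.** It is tempting to say that a raw change by arm would mostly reflect age mix. The documents do not show this. Allocation is randomised 1:1 within weight groups, and weight is likely to track age, which limits imbalance between arms. Standardised scores help interpretation across ages 5-17, but they are a preference, and raw centimetres and kilograms at baseline are not an error.

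**Completeness.** Detailed output specifications are in a separate document (SAP 1.1), some titles are redacted, and 5.9.3 introduces its vital signs as examples. These leave little room: the redacted table titles stand under exploratory efficacy, and SAP 4.4.2 and the limits in SAP Table 3 cover only blood pressure and pulse.

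**Conclusion.** The omission is real and limited. Measured height and weight after baseline have no table or listing among the legible titles in SAP Section 10. That falls short of Protocol 9.9, and SAP Section 6 does not acknowledge it. Followed as written, the plan would leave collected paediatric safety data unreported by arm.

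The point concerns completeness of safety reporting. It changes no efficacy estimate, and it does not rest on any suspected effect of the drug on growth. It should be corrected before the analysis, chiefly because the correction is cheap.

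It rests on two assumptions: that Section 10 is the SAP's full list of outputs apart from redacted entries, and that height and weight are among the other safety parameters of Protocol 9.9. Their place under Protocol 7.2.2 supports the second. The growth range of 4 to 7 cm/year serves only to judge where height change is worth tabulating.

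**What to change.** 1. In SAP 5.9, add height, weight and BMI to the safety variables, using the phase-specific baseline/Week 0 already defined there.
2. Summarise actual values and change from baseline/Week 0 to the end of phase by arm: weight in every phase (high dose only in the Open-label Phase), and height mainly in the Maintenance Phase. Preferably also give age- and sex-standardised z-scores against a reference that the sponsor names.
3. Add a by-subject listing of all height and weight values to Section 10.
4. Any threshold for notable weight loss is for the sponsor to choose; the documents give none.
5. If the sponsor prefers not to add these outputs, record and justify the omission in SAP Section 6.

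The cost is a few extra tables, one listing and some SAP wording, with no new data. The downside is noisy height change in the 8-week phases, where expected growth of about 0.6 to 1.1 cm is close to the 1 cm recording step.

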5.9.1 Adverse Events

Adverse events will be coded using Version 16.1 (or newer) of Medical Dictionary for Regulatory Activities (MedDRA). The number and percentage of subjects with an event, as well as the number of events will be reported for each summary.

An AE (classified by preferred term) that occurs during the study will be considered a treatment-emergent AE (TEAE) if it has a start date on or after the first dose of investigational product or if it has a start date before the date of the first dose of investigational product, but increases in severity on or after the date of the first dose of investigational product. If more than 1 AE with the same preferred term is reported before the date of the first dose of investigational product, then the AE with the greatest severity will be used as the benchmark for comparison to the AEs occurring during the study under the preferred term. An AE that occurs more than 7 days after the date of the last dose of investigational product of that phase will not be counted as a TEAE.

An overall summary of the number of subjects with TEAEs and number of TEAEs will be presented overall for the Overall Safety Analysis Set, an overall summary of the number of subjects with TEAEs and number of TEAEs will be presented for High-dose MMX only for Open Label Acute Phase Safety Analysis Set, and by treatment group and overall for the Double-blind Acute and Double-blind Maintenance Phase Safety Analysis Sets. The summary will include the number and percentage of subjects with any TEAEs, serious TEAEs, TEAEs related to investigational product, TEAEs leading to discontinuation of investigational product and TEAEs leading to death.

The number and percentage of subjects reporting TEAEs, as well as the number of events, will be tabulated by system organ class (SOC) and preferred term for Overall Safety Analysis set, the Double-blind Acute and Double-blind Maintenance Phase Safety Analysis Sets, and also for Open-label Acute Phase Safety Analysis Set.

The number and percentage of subjects reporting TEAEs will also be tabulated by SOC, preferred term, and maximum severity for Overall Safety Analysis set, Double-blind Acute and Double-blind Maintenance Phase Safety Analysis Sets, and also for Open-label Acute Phase Safety Analysis Set.

Treatment-emergent adverse events considered related to investigational product will also be summarized by SOC and preferred term for Overall Safety Analysis set, Double-blind Acute and Double-blind Maintenance Phase Safety Analysis Sets, and also for Open-label Acute Phase Safety Analysis Set.

If more than 1 AE occurs with the same preferred term for the same subject, then the subject will be counted only once for that preferred term using the most severe and most related occurrence for the summarization by severity and by relationship to investigational product.

The incidence of frequently occurring TEAEs ($\geq 5\%$ of subjects in any treatment arm) will be summarized by preferred term for Overall Safety Analysis set, the Double-blind Acute and Double-blind Maintenance Phase Safety Analysis Sets, and also for Open-label Acute Phase Safety Analysis Set.

TEAEs related to investigational product, serious TEAEs, TEAEs leading to discontinuation of investigational product, and serious TEAEs leading to death will be summarized by SOC and preferred term.

Treatment-emergent adverse events of special interest (including renal toxicity, hepatic toxicity, pericarditis, myocarditis, pancreatitis, gastritis, and cholecystitis) will also be summarized by SOC and preferred term for Overall Safety Analysis set, Double-blind Acute and Double-blind Maintenance Phase Safety Analysis Sets, and also for Open-label Acute Phase Safety Analysis Set.

Renal Toxicity

- Acute renal failure - (SMQ- Broad)
- Chronic kidney disease – (SMQ- Broad)

Hepatic Toxicity

- Drug related hepatic disorders- comprehensive search – (SMQ)
- Cholestasis and jaundice of hepatic origin (SMQ)
- Drug related hepatic disorders – severe events only (SMQ)
- Liver related investigations, signs and symptoms (SMQ)
- Liver related coagulation and bleeding disturbances (SMQ)

Pericarditis

- Pericarditis (PT)
- Pleuropericarditis (PT)

Myocarditis

- Myocarditis (PT)
- Allergic Myocarditis (PT)
- Eosinophilic myocarditis (PT)

Pancreatitis

- Acute pancreatitis (SMQ)

Gastritis

- Gastrointestinal nonspecific inflammation (SMQ)
- Gastrointestinal nonspecific dysfunction (SMQ)

Cholecystitis

- Cholecystitis (PT)
- Cholecystitis acute (PT)
- Cholecystitis chronic (PT)
- Cholecystectomy (PT)
- Cholecystocholangitis (PT)

Subject listings will be presented for all deaths, serious AEs (SAEs), and subjects withdrawn due to AEs.

